1. The primary endpoint of this study is whether mpMR parameters measured after 2 months of neoadjuvant ADT therapy (TP1) correlate with nadir PSA post 8-weeks of ADT. In addition, we will determine whether mpMR parameters in areas of tumor (T) in those who fail neoadjuvant ADT (defined as PSA end ADT values $>.3$ ng/ml) are different to those who respond to ADT (defined as PSA end ADT $\leq.3$ ng/ml).
2. A secondary endpoint of this study is whether mpMR parameters measured after 6 weeks of EBRT (TP2) and 8 weeks after completion of EBRT (TP3) correlate with end PSA (defined as PSA level immediately after EBRT treatment). In addition, we will determine whether mpMR parameters in areas of T in those likely to fail combined ADT/EBRT (defined as PSA end values $>.5$ ng/ml) are different to those of responders (PSA end values $\leq.5$ ng/ml).

IV Subject selection

1. Inclusion criteria:
 - a. Adult males with unfavorable intermediate- to high-risk localized disease identified as one of the following three categories for unfavorable intermediatehigh risk factors, but must have visible disease on baseline MRI.
 - i. Clinical or radiographic T2b-T4 primary tumor
 - ii. Gleason score 7-10 in any core
 - iii. PSA ≥ 10 prior to initiation of therapy
 - b. Patients are deemed suitable for therapy with ADT and EBRT.
 - c. Subjects must be able to provide informed written consent prior to study entry.
2. Exclusion criteria:
 - a. The standard exclusion criteria for MRI exams will apply which include patients with pacemakers, non-compatible intra-cranial vascular clips, inner ear implants, and severe claustrophobia.
 - b. Patients who because of age, general medical or psychiatric condition, or physiologic status unrelated to the presence of prostate cancer are unlikely to be candidates for repeat MRIs, or cannot give valid informed consent.
 - c. Patients unwilling or unable to undergo the ecoli placement or multiparametric MRI exam.
 - d. Patients with a history of allergic reaction to latex or Gadolinium containing intravenous contrast agents.

- e. Individuals with renal disease or other contraindications to gadolinium will be excluded. The BWH standard MRI contrast screening criteria will be used to establish renal status.
- f. Patients who have had prior prostatectomy or prior androgen therapy.

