2. PSA

Serum PSA will be checked at baseline by treating physician, prior to commencing therapy. Serum PSA will also be subsequently checked on the same day as each follow-up MR is performed, i.e. TP 1,2 and 3, and right after finishing EBRT.

Parking at BWH for time spent for all 4 follow-up serum PSAs will be paid for.

3. Prostate MRI

The baseline prostate MRI is standard of care management, ordered by the radiation oncologist for staging and for EBRT planning. The 3 follow-up MRIs (at TP 1,2 and 3) are not standard of care management, and will be paid for by an NIH grant. However, all of the follow up prostate MRIs will use a standard BWH Radiology Department prostate non-endorectal coil MRI protocol. Subjects will need, to complete health screening and renal assessment forms completed prior to the MRI to determine if the patient is able to receive gadolinium. Blood results measuring renal function within a 3-week window prior to MR must be available, and if necessary, blood will be drawn to measure kidney function prior to administration of gadolinium. Subjects will be positioned lying on their back within the MRI magnet, which is a large cylindrical tube that allows strong magnetic fields to pass through the body. Earplugs and a padded table will be provided for the subject's comfort. A radio frequency receiver coil encased in a plastic mold called a phased-array coil will be positioned around the subject's pelvis. An endorectal coil will NOT be used for this study, as the endorectal probe will distort the prostate (making correlation with CT for planning difficult) and because of the risk of proctitis during EBRT.

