Zelevsky et al. report that 10-year relapse-free survival among patients with PSA nadir ≤ 0.3 was 74.3%, compared with 57.7% for patients with higher PSA nadir values ($P = 0.001$, $N = 1045$). In order to assess power for a test of whether mpMR parameters measured after 2 months neoadjuvant ADT therapy alone correlate with nadir PSA post 8-weeks of ADT therapy, we will make use of published data on the correlation between ADC change and nadir PSA. Foltz et al.[24] observed a correlation of 0.25 for nadir PSA with ADC percent change, between 6 weeks and the pre-RT baseline ($N = 10$). With 30 subjects, we anticipate 80% power to detect an absolute correlation of 0.49 or greater. Although this is greater than the correlation Foltz observed, we note that with a sample of size 10, using Fisher's transformation, an approximate 95% confidence interval for Foltz's estimate is (-0.45, 0.76), a wide interval which includes 0.49.

2. Within-Patient ADC Changes

Foltz et al.[24] reported a change in ADC between six weeks RT and baseline of -0.29 in tumor (2.8%, N = 36) and -0.56 in healthy tissue (N=10), with SDs of 0.23 and 0.18, respectively (in units of 10^{-3} mm²/s). Using the average variance above, we estimate a SD for ADC of 0.20. With N = 30 subjects, using this SD, we expect to have 80% power to detect a significant within-subject absolute difference in ADC between two time points of 0.14 or greater, based on a paired t-test at the 0.05 twotailed significance level, corrected for the 6 pairs of time points to be considered. This is much smaller than the difference of 0.81 observed in healthy tissue described by Barrett et al.[23], but larger than the very small difference of 0.03 that they observed in tumor. Foltz et al. observed changes in ADC between 4 weeks and baseline of 0.107 (B = 600) and 0.117 (B = 1200), both of which are less than 0.14.

3. Comparison of Normal Tissue ADC With Tumor

For comparisons between tumor and normal tissue, with 30 subjects we expect 80% power to detect an absolute difference in mean ADC of 0.19 or greater, based on a two-tailed two-sample t-test, adjusted for multiple comparison of time-points. Barrett's group observed a mean difference in ADC between tumor and healthy tissue of 0.20.

4. Comparison of ADC Changes between Patients who Fail Treatment and Those who do not.

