We estimate that 25% of men with grade T2c or greater cancer will have end PSA greater than 0.5, and will fail therapy. Barrett et al. reported a change in ADC between three months of ADT and a preADT baseline in tumor of -0.028 with a SD of 0.227 (N = 35), in 20 patients with tumor of stage T2c or greater. We therefore estimate that ultimately 25% of these patients failed. We assume that the ADC changes in patients who fail and patients who do not fail are both normally distributed, with the same SD but different means. We estimate this SD from the Barrett et al. data as $0.227/\sqrt{0.25^2+0.75^2} = 0.287$. In our study, with 30 patients, we expect approximately 8 treatment failures. Assuming 8 failures and a SD of 0.287, we will have 80% power to detect an absolute difference between the mean ADC change among those who fail treatment and those who do not of 0.51 SDs, or $0.51 \times 0.287 = 0.15 \times 10^{-3}$ mm²/s change in ADC. Barrett observed a baseline ADC mean in tumor of 1.006, hence we expect to be able to detect a change from baseline and 3-months ADT in ADC of approximately +/- 15% or greater.

5. Descriptive statistics will be used to enumerate the rectal V70's achieved using MRI versus CT data.

VIII Risks and Discomforts

Participants in this study will undergo a total of 3 follow up prostate MRIs. (Baseline standard of care prostate MRI prior to initiating therapy will be ordered by the treating physician). All MRIs will use a standard routine prostate MRI protocol without the use of an endorectal coil. Patients will receive Magnavist 0.1mmol/kg intravenously for each study, so renal function will need to be checked prior to

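### Section VII.3 plans a two-sample t-test for tumor versus normal ADC, although both tissues appear to come from the same 30 men, so the contrast should be paired

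*Combined protocol and SAP*

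**What the plan says.** Section VII.3 states: "For comparisons between tumor and normal tissue, with 30 subjects we expect 80% power", for a difference in mean ADC of "0.19 or greater, based on a two-tailed two-sample t-test, adjusted for multiple comparison of time-points". It gives no number per group, no SD and no divisor for the multiplicity adjustment. It does not mention pairing or correlation, and no other section names a test for this contrast.

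The surrounding text matters in four places:

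- Section IV (inclusion criterion 1a): men "must have visible disease on baseline MRI". No group without tumor is enrolled.
- Section VII.4: "In our study, with 30 patients, we expect approximately 8 treatment failures", which describes a single cohort.
- Section VI.3: "The 3 follow-up MRIs (at TP 1,2 and 3) are not standard of care management". With the baseline scan, each man has four scans.
- Section VII.2: changes between time points are assessed "based on a paired t-test at the 0.05 twotailed significance level", corrected for six pairs of time points, and "we estimate a SD for ADC of 0.20". The plan therefore already pairs within-subject contrasts in the preceding subsection.

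**The concern.** A two-sample t-test is valid when the two sets of values are independent. If each man supplies a tumor value and a normal-tissue value from the same scan, the two are correlated to some degree (rho), and the test's standard error omits that term. The test then holds its nominal level only if rho is zero.

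Positive rho is the more plausible case, because scanner, session and patient effects are shared. The test is then conservative: intervals are too wide and information already collected is lost. If rho is negative, the type I error exceeds nominal. At stake is the validity and efficiency of this one contrast.

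**Working it through.** **Inputs.** From VII.2: component SDs 0.23 (tumor) and 0.18 (healthy tissue), in 10⁻³ mm²/s. Average-variance SD = √((0.23² + 0.18²)/2) = 0.2065, which the plan reports as 0.20. From VII.3: 30 subjects, 80% power, 0.19. Assumed: that VII.3 reuses this SD, that the divisor is 4 (scans) or 6 (as in VII.2), and rho, which is shown over a range.

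**Step 1: reproduce 0.19.** Two-sided noncentral t at 80% power; detectable difference = d × SD, with SD 0.20 to 0.2065.

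| Layout | d at 0.05/6 | Difference | d at 0.05/4 | Difference |
|---|---|---|---|---|
| 30 tumor, 30 normal (df 58) | 0.926 | 0.185–0.191 | 0.886 | 0.177–0.183 |
| 15 tumor, 15 normal (df 28) | 1.356 | 0.271–0.280 | 1.292 | 0.258–0.267 |

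The plan's figure is matched by 30 values per tissue at 0.05/6. A 15/15 split would need an SD of 0.19/1.356 = 0.14 or 0.19/1.292 = 0.15. The same SD and divisor also reproduce the 0.14 in VII.2: 0.676 × 0.20 to 0.2065 = 0.135 to 0.140, where 0.676 is the paired effect size for n = 30 at 0.05/6. One set of inputs therefore explains both figures, with 30 men contributing a value to each tissue.

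**Step 2: standard error.** With n pairs and a common SD, the true variance of the mean difference is 2·SD²(1 − rho)/n. The two-sample test estimates 2·SD²/n. The ratio of its standard error to the true one is 1/√(1 − rho): 1.20 at rho 0.3, 1.41 at 0.5 and 0.88 at -0.3.

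**Step 3: type I error of the two-sample test** (simulation, 30 pairs, equal SDs).

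| rho | Nominal 5% | Nominal 1.25% (0.05/4) |
|---|---|---|
| -0.3 | 8.5% | 2.8% |
| 0 | 5.0% | 1.25% |
| 0.3 | 2.0% | 0.3% |
| 0.5 | 0.7% | 0.07% |

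The paired test stays at nominal for every rho. With unequal SDs of 0.23 and 0.18 the pattern is the same. Neither these rates nor the standard-error ratios depend on the size of the SD.

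**Step 4: power for a difference of 0.19** (SD 0.2065), two-sample against paired.

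| rho | 0.05/4 | 0.05/6 |
|---|---|---|
| 0 | 83% vs 81% | 79% vs 76% |
| 0.3 | 87% vs 94% | 83% vs 91% |
| 0.5 | 91% vs 99% | 87% vs 98% |

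**Step 5: detectable difference with a paired test.** Difference = dz × SD × √(2(1 − rho)), n = 30, dz = 0.645 at 0.05/4, SD 0.20 to 0.2065.

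- rho -0.3: 0.645 × SD × 1.612 = about 0.21
- rho 0: 0.645 × SD × 1.414 = 0.18–0.19
- rho 0.3: 0.645 × SD × 1.183 = 0.15–0.16
- rho 0.5: 0.645 × SD × 1.000 = 0.13

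**The case against.** VII.3 is a power statement, not a full analysis specification, and its figure does no harm. A paired calculation at rho 0 also gives about 0.19 (0.191 to 0.198 at 0.05/6), so assuming independence is a cautious planning choice whenever rho is positive. The test is then conservative, and power for 0.19 still exceeds 80% (83% to 91% for rho 0.3 to 0.5). Nothing in the documents points to a negative rho.

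Much of this stands. The 0.19 is not an arithmetic error, and the likelier consequence is lost efficiency rather than false positives. However, VII.3 is the only place that names a test for this contrast, so an analyst following the plan would run it.

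Two caveats on the numbers also stand. First, the 0.20 comes from SDs that VII.2 reports with a change in ADC between two times; no single-scan SD for either tissue is given. The power figures and paired detectable differences are therefore illustrative. Second, VII.3 does not state its divisor: 6 reproduces 0.19, while 4 gives 0.18. Using 4 is a separate choice, based on the number of scans, and does not follow from pairing.

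**Conclusion.** The concern holds and is minor. VII.3 names an independent-samples test for what appears to be a within-man comparison. That the same men supply both tissues is an inference, but the single cohort, the visible-disease criterion, the absence of controls and the plan's own 0.19 all support it.

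The direction and size of the error depend on rho, which the documents do not give. The two-sample standard error is 20% too large at rho 0.3, 41% too large at 0.5, and 12% too small at -0.3. The contrast is not a section III endpoint, and neither the sample size of 30 nor the endpoint analyses are affected.

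**What to change.** In VII.3, replace the two-sample t-test with a paired t-test of tumor minus normal ADC within each man at each scan. State the divisor explicitly: 0.05/4 if baseline and TP1 to TP3 are all compared. Give the SD and its source, and restate the detectable difference over a range of assumed rho, as in the last step of the working. Say that both tissues are measured in the same men; if they are not, say so and justify the independent test. Where a man has more than one tumor region, state how they are reduced to one value per scan.

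If a mixed model is preferred, so as to keep men with incomplete pairs, it needs man-by-tissue and man-by-scan random terms or an unstructured covariance. A random subject intercept alone forces one common correlation on all of a man's readings and is not enough.

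The cost is wording only, with the same scans and data. If rho is in fact zero, the paired test loses 2 to 3 points of power (81% against 83% at 0.05/4; 76% against 79% at 0.05/6). Men lacking either tissue value at a scan drop out of that scan's paired test.

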Foltz et al. have looked at the very early post-radiotherapy changes in the prostate every 2 weeks up until 8 weeks of EBRT, and found that ADC was a possible candidate for early response to therapy, the optimal scan time being week 6 of EBRT[24]. Park et al have shown that ADC values in regions of tumor increased 1 and 3 weeks after initiating EBRT, and one month after completion of EBRT[25].

Specific to DCE, there is known to be an anti-angiogenic role for ADT in the prostate (androgen ablation has been shown to suppress glandular epithelial production of VEGF and induce apoptosis of endothelial cells). As PSA gene expression is down-regulated by ADT, PSA reduction post ADT may be secondary to androgen suppression rather than tumor cell death. It is therefore possible that DCE may act as a stronger surrogate for angiogenesis, rather than PSA.

There has been a pre-clinical study (on prostate xenograph models) evaluating a combination of parameters (ADC, DCE, tumor volume and PSA) which successfully predicted treatment response to a combination of ADT and radiotherapy, with a correlation coefficient of 0.85[26]. However, to our knowledge, no study has yet looked at a role for mpMRI in evaluating the effect of combined ADT and EBRT on prostate mpMR in humans. Nor has there been any work published on correlating PSA end with prostate mpMR, to determine if mpMR may act as an early biomarker in determining those who would benefit from long-term androgen suppression. We therefore propose to evaluate mpMR in response to combined therapy (ADT and EBRT), and to correlate quantitative mpMR parameters at early timepoints, with PSA end and PSA nadir.

II Specific Aims

1. The primary aim of this study is to explore the feasibility of mpMR as an early imaging biomarker to assess response of intermediate- and high-risk prostate cancer during treatment with neoadjuvant ADT.
2. A secondary aim is to explore the feasibility of mpMR as an imaging biomarker to assess response of bulky localized prostate cancer to combined ADT/EBRT.

3. To ascertain if the information provided using the non-ecoli 3 Tesla MRI images prior to starting EBRT can supplement CT information for Radiation Treatment (RT) planning purposes in men who are planning to undergo RT for prostate cancer.

III Study endpoints

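### VII.4 applies a failure rate stated for T2c-or-greater tumors to all 30 men, although eligibility is wider; the count of 8 needs a range on both sides, with the detectable difference restated across it

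*Combined protocol and SAP*

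**What the plan says.** Section VII.4 plans the comparison of ADC change between men who fail treatment and men who do not. It ties its failure rate to a stage: "We estimate that 25% of men with grade T2c or greater cancer will have end PSA greater than 0.5". It takes the SD of ADC change from a cited feasibility study of ADT, "in 20 patients with tumor of stage T2c or greater", and assigns that cohort the same rate: "We therefore estimate that ultimately 25% of these patients failed". It then turns to its own sample: "In our study, with 30 patients, we expect approximately 8 treatment failures". The power statement follows: "Assuming 8 failures and a SD of 0.287, we will have 80% power to detect an absolute difference between the mean ADC change" between the two groups of 0.51 SD, or 0.15 × 10^-3 mm²/s, which the section equates to roughly 15% of a baseline tumor ADC of 1.006.

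Section IV.1 defines a different population. A man with disease visible on baseline MRI qualifies on any one of three features: "Clinical or radiographic T2b-T4 primary tumor", "Gleason score 7-10 in any core", or PSA of 10 or more before therapy. The study flyer and the template email to physicians join the three with an explicit 'or'.

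**The concern.** The 25% belongs to men with T2c or greater tumors, and the cited cohort matches that description. The 30 men of this study need not. A T2b tumor is eligible, and Gleason score or PSA alone admits a man with no lower limit on T stage. No section gives the expected share of T2c-or-greater men, sets a minimum share, or argues that 25% holds for the wider group.

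The failure count fixes the size of the smaller group, and the smaller group largely determines what a comparison of 30 men can detect. If the count is an assumption borrowed from another population, the power statement built on it is too. A reader of a null result would then not know which differences the study could have seen.

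**Working it through.** **Inputs.** From VII.4: failure rate 25% (T2c or greater), 30 patients, 8 failures, SD 0.287, 80% power, detectable difference 0.51 SD, baseline tumor ADC 1.006. VII.4 states no alpha; two-sided 0.05 is assumed, the level VII.2 uses before its multiplicity correction.

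**1. Reproducing the plan's count.** 0.25 × 30 = 7.5, rounded to 8. The T2c-or-greater rate was therefore applied unchanged to every enrolled man. The SD also reproduces as written: 0.227 / √(0.25² + 0.75²) = 0.227 / √0.625 = 0.287. In that step the 25% is applied to the cited T2c-or-greater cohort, so rate and population agree; the carry-over affects the group sizes. The value 0.287 is taken as given here.

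**2. How far the count could move.** Let s be the share of enrolled men with T2c or greater and q the failure rate in the others. Then expected failures = 30 × [0.25s + q(1 − s)]. Neither s nor q is in the documents, so these values are illustrations only:

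- s = 0.5, q = 0.05: 30 × (0.125 + 0.025) = 4.5
- s = 0.5, q = 0.15: 30 × (0.125 + 0.075) = 6.0
- s = 0.5, q = 0.25: 30 × (0.125 + 0.125) = 7.5
- s = 0.5, q = 0.40: 30 × (0.125 + 0.200) = 9.75
- s = 0.25, q = 0.05: 30 × (0.0625 + 0.0375) = 3.0
- s = 0.25, q = 0.45: 30 × (0.0625 + 0.3375) = 12.0

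The count falls below 7.5 when q is below 25% and rises above it when q is above 25%. The documents do not say which applies.

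**3. Detectable difference over a range of counts.** For k failures and 30 − k non-failures, the normal approximation in SD units is (1.960 + 0.842) × √(1/k + 1/(30 − k)). For k = 8 this is 2.802 × √(0.125 + 0.0455) = 2.802 × 0.413 = 1.16. The noncentral-t calculation, which suits groups this small, gives 1.20.

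| Failures / others | Normal (SD) | t-test (SD) | × 0.287 (10^-3 mm²/s) | Share of 1.006 | Power at 0.51 SD (t) |
|---|---|---|---|---|---|
| 4 / 26 | 1.51 | 1.56 | 0.45 | 44% | 15% |
| 6 / 24 | 1.28 | 1.33 | 0.38 | 38% | 19% |
| 8 / 22 | 1.16 | 1.20 | 0.34 | 34% | 22% |
| 10 / 20 | 1.09 | 1.12 | 0.32 | 32% | 25% |
| 12 / 18 | 1.04 | 1.08 | 0.31 | 31% | 26% |

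**4. The plan's 0.51 SD.** It does not reproduce for 8 versus 22. A one-sided test would still need 1.05 SD, with 33% power at 0.51 SD. The most favourable split, 15 versus 15, needs 2.802 × √(2/15) = 1.02 SD even under the normal approximation, so no division of 30 men reaches 0.51. The figure coincides with a one-sample normal calculation on all 30 men, 2.802 / √30 = 0.511; the plan does not say how it was obtained.

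**The case against.** A reader might infer a stronger point: that the trial enrols less advanced men than the 25% describes, and so will see fewer than 8 failures. The documents do not support a direction. Eligibility reaches T4, Gleason 10 and any PSA from 10 upward, and every man must have unfavorable intermediate- to high-risk disease visible on MRI. The background section on EBRT and ADT lists high PSA, high Gleason score and T2b or higher together as features of high-risk men and does not rank T stage above the other two. A man below T2c with a high Gleason score or PSA could fail more often than 25%. Nor is it evidence of a mismatch that, at a true rate of 25%, at least 8 failures occur with probability only 49% (1 − 0.514). That is ordinary binomial variation around 7.5, and the plan says approximately.

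A reader might also link this to Aim 2, which is to "explore the feasibility of mpMR as an imaging biomarker to assess response of bulky localized prostate cancer to combined ADT/EBRT". The word for bulk is undefined and does not recur in the endpoints, the eligibility criteria or VII.4. It is a wording point and does not bear on the failure count.

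Two further objections stand in part. First, the consequence is limited. The 25% concerns end PSA above 0.5, the additional comparison under the secondary endpoint, in a study whose first two aims are to explore feasibility. The correlation that leads the primary endpoint uses all 30 men and no failure count. Even so, VII.4 makes an explicit 80% power claim, and that claim should rest on its own population. Second, the failure rate is the smaller problem in that claim. Going from 8 failures to 4 raises the detectable difference by a factor of 1.56 / 1.20 = 1.30, whereas at exactly 8 the stated figure is already too small by 1.20 / 0.51, about 2.3. This is a reason to correct both together. A recalculation must start from a failure count, and the present one was stated for other men.

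**Conclusion.** The point holds without a direction. VII.4 carries a T2c-or-greater failure rate over to a wider eligible population, and nothing in the documents supports the transfer or shows whether 8 is too many or too few. Over 4 to 12 failures the two-sample detectable difference is 1.56 to 1.08 SD, or 0.45 to 0.31 × 10^-3 mm²/s, against the stated 0.51 SD and 0.15. Power at the stated difference is about 15% to 26%, not 80%.

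These figures assume a two-sided alpha of 0.05, equal SDs in the two groups and, for the ADC units, the plan's 0.287. The SD-unit results do not depend on 0.287. The range of 4 to 12 is illustrative, since the documents offer no basis for a narrower one.

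**What to change.** In VII.4:

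- State that 25% refers to men with T2c or greater tumors.
- Describe the failure count in the population admitted by IV.1 as an assumption, with a range on both sides of 8 (for example 4 to 12 of 30). If the sponsor has an expected mix of stage, Gleason score and PSA, give it with its source.
- State the alpha level and sidedness.
- Replace the single 0.51 SD figure, and the 0.15 and 15% derived from it, with the two-sample detectable difference over that range: 1.56 SD (0.45) with 4 failures, 1.20 SD (0.34) with 8 and 1.08 SD (0.31) with 12.

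Optionally, align the wording of Aim 2 with the population in IV.1.

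The cost is a text edit and a less favourable stated figure. Eligibility, sample size and study procedures stay as they are.

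### Section VII.4 derives the within-group SD of 0.287 from a formula that does not fit its own two-group model; that model caps the SD at 0.227

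*Combined protocol and SAP*

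**What the plan says.** Section VII.4 of the combined protocol and SAP gives the power for comparing ADC change between patients who fail treatment and those who do not.

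- **Source figure.** It comes from a cited study of ADT and is a mean change "tumor of -0.028 with a SD of 0.227 (N = 35), in 20 patients with tumor of stage T2c or greater".
- **Failure rate.** The plan carries a 25% rate over to that study: "We therefore estimate that ultimately 25% of these patients failed".
- **Model.** ADC changes in the two groups "are both normally distributed, with the same SD but different means".
- **Common SD.** It is obtained as "0.227/\sqrt{0.25^2+0.75^2} = 0.287", with no reason given for the divisor.
- **Use.** "In our study, with 30 patients, we expect approximately 8 treatment failures" The plan then states: "Assuming 8 failures and a SD of 0.287, we will have 80% power to detect an absolute difference". The difference is given as 0.51 SD, which becomes 0.15 (in 10^-3 mm²/s) and about 15% of a baseline tumor mean of 1.006.

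**The concern.** Splitting a sample into two groups with different means can only lower the SD or leave it unchanged, because part of the total spread is the gap between the means. The plan's step raises the SD from 0.227 to 0.287. It would do so even if the two groups were identical: labelling a homogeneous sample 25/75 would inflate its SD by 26%.

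The 0.287 feeds the 80% power statement, the 0.15 and the 15%. This is the only power statement in the plan for a comparison of failures with responders. It uses the end-PSA cut-off of 0.5 from the secondary endpoint; the analogous comparison in the primary endpoint, at 0.3, has no calculation of its own. What is at stake is whether readers are told correctly what 30 patients can show. The error also sits beside a second one in the same sentence that acts in the opposite direction, so correcting either alone still gives a wrong figure.

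**Working it through.** **Inputs, all from Section VII.4 unless noted.** Overall SD 0.227 (35 observations, 20 patients); failure proportion p = 0.25; 8 failures, hence 22 non-failures; power 80%; multiplier 0.51; baseline mean 1.006. Section VII.4 gives no significance level. Two-sided 0.05 is assumed here, as used in Section VII.2, and alternatives are shown in step 6.

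**1. Reproduce the plan's figures.** sqrt(0.25² + 0.75²) = sqrt(0.625) = 0.791, and 0.227 / 0.791 = 0.287. Then 0.51 × 0.287 = 0.146, and 0.146 / 1.006 = 14.5%. The arithmetic reproduces.

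**2. What the divisor describes.** If X and Y are independent with SD σ, then 0.25X + 0.75Y has SD σ × sqrt(0.25² + 0.75²). A simulation with σ = 0.287 gives 0.227 for that sum. No patient's ADC change is such a sum.

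**3. The variance under the stated model.** Each patient belongs to one group. With common SD σ and mean difference Δ:

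overall variance = 0.25σ² + 0.75σ² + 0.25 × 0.75 × Δ² = σ² + 0.1875Δ²

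so σ = sqrt(0.227² − 0.1875Δ²).

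| Δ | σ |
|---|---|
| 0 | 0.227 |
| 0.10 | 0.223 |
| 0.15 | 0.218 |
| 0.20 | 0.210 |
| 0.25 | 0.200 |

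For σ to be 0.287 with an overall SD of 0.227, Δ² would have to be (0.227² − 0.287²) / 0.1875 = −0.164, which is impossible. Simulated 25/75 mixtures (2,000,000 draws) with σ = 0.287 have overall SD 0.287, 0.294 and 0.315 at Δ = 0, 0.15 and 0.30.

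**4. Size of the error.** SD ratio at least 1 / sqrt(0.625) = 1.26; variance ratio at least 1 / 0.625 = 1.60. At the plan's own Δ of 0.15, 0.287 / 0.2175 = 1.32.

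**5. The multiplier in the same sentence.** For 8 versus 22, the normal approximation gives (1.960 + 0.842) × sqrt(1/8 + 1/22) = 1.16 SD, and the t-test gives 1.20 SD. The plan's 0.51 equals (1.960 + 0.842) / sqrt(30), a one-sample result. Solving σ and Δ jointly for a multiplier k gives σ = 0.227 / sqrt(1 + 0.1875k²) and Δ = kσ. For k = 1.20, σ = 0.201 and Δ = 0.24.

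| Correction made | Detectable difference | % of 1.006 |
|---|---|---|
| None (plan) | 0.146 | 14.5 |
| SD only (0.51 kept) | 0.113 joint; 0.116 with σ = 0.227 | 11.2; 11.5 |
| Multiplier only (σ = 0.287) | 0.34 | 34 |
| Both | 0.24 joint; 0.27 with σ = 0.227 | 24; 27 |

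At a true difference of 0.15, the two-sided t-test for 8 versus 22 has about 23% power with SD 0.287, 34% with 0.227 and 36% with 0.2175, not 80%.

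**6. Sensitivity to the unstated significance level (both corrections made).** One-sided 0.05 gives 0.22 (joint) to 0.24 (σ = 0.227). Two-sided 0.05/6, the six-pair correction named in Section VII.2, gives 0.29 to 0.35.

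**The case against.** Four points can be made for the plan.

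- **The error is conservative.** An SD that is too large makes the study look less sensitive than it is. This stands: with either multiplier, 0.287 gives a larger detectable difference than the correct SD.
- **Most of the shortfall comes from the multiplier.** This also stands. The move from 0.15 to 0.24–0.27 is driven by replacing 0.51. But repairing only the multiplier would give 0.34, which overstates the detectable difference by 26% (0.344 / 0.272) to 43% (0.344 / 0.241). The SD must be corrected as well.
- **0.227 is itself an estimate.** With sample degrees of freedom, a pooled within-group SD could reach 0.227 × sqrt(34/33) = 0.230, or 0.233 if N is 20. A normal-theory 95% interval for the true overall SD is about 0.18–0.30 (N = 35) or 0.17–0.33 (N = 20), so a true SD near 0.287 is not excluded by the data. Also, 35 observations in 20 patients may not give a patient-level SD. These are reasons to choose a cautious planning value openly. The plan makes no such argument and presents 0.287 as derived.
- **The study is exploratory.** The aims concern feasibility, no analysis or decision uses this SD, and nothing shows that the sample size of 30 was derived from it. This limits the consequence to the accuracy of the power statement.

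None of these points supports the formula, and nothing elsewhere in the document justifies it.

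**Conclusion.** The concern holds. Section VII.4 states a two-group mixture and then uses a formula for something else. Taking 0.227 as the overall SD, as the plan does, the common within-group SD is at most 0.227, and the stated 0.287 is too large by at least 26% (variance by at least 60%). The bound is exact for that algebra; it does not allow for sampling error in 0.227.

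The stated 0.15 and 15% are therefore unsupported. Assuming a two-sided 0.05 t-test with 8 failures and 22 non-failures, 80% power corresponds to roughly 0.24–0.27, or 24–27% of the baseline mean. The SD error works against the plan's apparent sensitivity and the multiplier error works for it. The multiplier error is the larger, so the net effect is an over-optimistic claim.

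**What to change.** In Section VII.4, replace the printed formula with σ = sqrt(0.227² − 0.25 × 0.75 × Δ²), or use 0.227 and say that it is the ceiling under the model. If the sponsor prefers a larger value to allow for uncertainty in 0.227, state that as a planning choice and give the reason.

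In the same edit, state the significance level and sidedness, recompute the detectable difference with the two-sample calculation for 8 versus 22, and restate the percentage of the 1.006 baseline. The SD and the multiplier should be changed together.

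The cost is one formula and the figures that follow from it. There is no operational cost.
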